12.5.1.3 Expansion (Part 2)

MDS symptoms and fatigue

The following analyses will be performed:

• Changes from baseline to post-baseline in fatigue using the FACIT-Fatigue

12.5.2 Safety endpoints

Safety analyses will be summarized for the safety set of the Safety run-in (Part 1) and Expansion (Part 2). Safety data will be provided by dose level of sabatolimab in the Safety run-in part.

Safety summaries (tables, figures) include only data from the on-treatment period with the exception of baseline data which will also be summarized where appropriate (e.g. change from baseline summaries). In addition, a separate summary for death including on treatment and post treatment deaths will be provided. In particular, summary tables for adverse events (AEs) will summarize only on-treatment events, with a start date during the on-treatment period (treatment-emergent AEs).

The overall observation period will be divided into three mutually exclusive segments:

1. Pre-treatment period: from day of participant's informed consent to the day before first administration of study treatment

2. On-treatment period: from date of first administration of study treatment to 30 days after date of last administration of study treatment

3. Post-treatment period: any observation starting at day 31 after last administration of study treatment

An overall safety period will be defined from date of first administration of study treatment to 150 days after the last dose of sabatolimab.

Adverse events

Summary tables for adverse events (AEs) will include only AEs that started or worsened during the on-treatment period. The number (and percentage) of participants with treatment emergent adverse events will be summarized by primary system organ class, preferred term and maximum severity.

Separate summaries will be provided for study medication related adverse events, death, serious adverse events, other significant adverse events leading to discontinuation, and adverse events leading to dose adjustment.

Serious adverse events and non-serious adverse events will be tabulated. All deaths (on-treatment and post-treatment) will be summarized.

In addition, all AEs and SAEs which started during the overall safety period will be summarized. All reported AEs will be listed and those that started during the pre-treatment, overall safety period and post-treatment period will be flagged.

Vital signs

All vital signs abnormalities will be summarized by visit.

12-lead ECG

HR PR, and QTcF will be obtained from 12-lead ECGs for each participant at screening and during the study. ECG data will be read and interpreted centrally.

Categorical analysis of QTcF interval and HR data will be based on the summary of number of participants meeting or exceeding predefined limits.

Clinical laboratory evaluations

Grading of laboratory values will be assigned programmatically as per National Cancer Institute (NCI) Common Terminology Criteria for Adverse Events (CTCAE) version 5.0. The calculation of CTCAE grades will be based on the observed laboratory values only, clinical assessments will not be taken into account.

CTCAE Grade 0 will be assigned for all non-missing values not graded as 1 or higher.

For laboratory tests where grades are not defined by CTCAE version 5.0, results will be categorized as low/normal/high based on laboratory normal ranges.

For laboratory tests where grades are defined by CTCAE v5.0:

• Shift tables using CTCAE v5.0 grades to compare baseline to the worst on-treatment value

For laboratory tests where grades are not defined by CTCAE v5.0:

• Shift tables using the low/normal/high/ (low and high) classification to compare baseline to the worst on-treatment value

Other safety evaluations

ECOG PS

ECOG PS will be summarized at each timepoint during the study.

12.5.3 Pharmacokinetics

The respective Pharmacokinetic Analysis Set (PAS) for sabatolimab and venetoclax from Safety run-in (Part 1) and Expansion (Part 2) will be used in all pharmacokinetic data analysis.

Sabatolimab and venetoclax drug concentrations

Sabatolimab and venetoclax concentration data will be listed by participant, and visit/sampling time point. Descriptive summary statistics for sabatolimab and venetoclax concentrations will be provided by visit/sampling time point. Summary statistics will include mean (arithmetic and geometric), SD, CV (arithmetic and geometric), median, minimum, and maximum, as well as the frequency (n, %) of concentrations below the lower limit of quantification (LLOQ) and reported as zero. Values below the LLOQ will be treated as missing for the calculation of the geometric means and geometric CV%. PK parameters (the minimum observed plasma or serum drug concentration (Cmin or Ctrough) will be estimated and reported. Missing values for any PK parameters or concentrations will not be imputed and will be treated as missing.

All concentration data for sabatolimab and venetoclax vs. time profiles will be displayed graphically.

As the half-life of venetoclax is approximately 26 hours, the sample collected at Cycle 1 Day 8 will be considered as the baseline venetoclax concentration at steady state before any dose administration of sabatolimab. The impact of sabatolimab on the venetoclax concentrations may be assessed by comparing concentrations before and after sabatolimab.

Population pharmacokinetic analysis

If data permit, a mixed-effects model may be applied to the serum sabatolimab concentrationtime data from this study along with other studies to generate post-hoc estimates of pharmacokinetic parameters using appropriate software to characterize sabatolimab exposure and to determine the effects of intrinsic (i.e. demographic factors) and extrinsic covariates (e.g. combination partners) on sabatolimab exposure. If there is sufficient data for analysis, the details of the population pharmacokinetic analyses may be provided in a separate reporting and analysis plan, and the results may be reported in a separate population pharmacokinetic report.

12.7 Interim analyses

No formal interim analysis is planned for this trial. During the Expansion (Part 2), a periodic safety review by the Steering Committee will occur approximately every 6 months.

In the Safety run-in (Part 1), the first safety review meeting will be conducted after participants included in the first cohort (N=6 with at least 3 evaluable participants treated with sabatolimab at the 400 mg Q4W) have completed 2 cycles of treatment. If the 400 mg Q4W dose of sabatolimab is considered to be safe in combination with venetoclax and azacitidine guided by the Bayesian analysis based on the incidence of dose limiting toxicity (DLT) data as well as all available safety, clinical pharmacology and tolerability data a second cohort with 12 participants will be opened (sabatolimab at 800 mg Q4W), otherwise the study will be stopped.

After completion of 2 cycles of treatment with at least 9 evaluable participants, the second safety review meeting will take place. The decision will be made based on DLT observation and the Bayesian model to open the Expansion (Part 2) (or not) at this dose level (sabatolimab at 800 mg Q4W) in combination with venetoclax and azacitidine. If sabatolimab 800 mg Q4W is considered to be safe then Expansion (Part 2) will be opened at the same dose level (800 mg Q4W). Otherwise the study will be stopped.

The primary analysis on CR rate will be performed after last participant have completed 6 cycles of treatment with sabatolimab + azacitidine + venetoclax or discontinued earlier. A final analysis will be performed after last enrolled participant have been followed for 3 years or discontinued study earlier. Formal testing of the primary endpoint with full level alpha will be performed at the primary analysis. If required or requested by Health Authorities, updated analyses after the primary CR rate analysis may be conducted prior to the final analysis.

12.8 Sample size calculation

12.8.1 Primary endpoint(s)

12.8.1.1 Safety run-in (Part 1)

No formal statistical power calculations to determine sample size were performed for this part of the study. In case the starting dose (sabatolimab 400 mg Q4W (N=6)) with the fixed dose combination of azacitidine plus venetoclax is confirmed to be safe and tolerated for at least 3 evaluable participants, another cohort will be opened at 800 mg of sabatolimab Q4W (N=12) with fixed dose of venetoclax plus azacitidine with at least 9 evaluable participants. Otherwise, the study will be stopped.

In total, the Safety run-in (Part 1) is expected to enroll approximately 18 participants (6 participants for cohort 1 (Sabatolimab (400 mg Q4W) and 12 participants for cohort 2 (800 mg (Q4W)) in order to have at least 12 evaluable participants (3 evaluable participants in cohort 1 and 9 evaluable participants in cohort 2).

12.8.1.2 Cohort 2 of Safety run-in (Part 1) and Expansion (Part 2) (CR primary analysis)

The sample size calculation is based on the Complete Remission (CR) rate (primary efficacy endpoint) for participants treated with sabatolimab 800 mg Q4W from Safety run-in (Part 1)

and Expansion (Part 2). The hypotheses to be tested and details of the testing strategy are described in Section 12.4.2.

Based on available data (Wei et al 2019), the CR rate with the combination azacitidine and venetoclax is expected to be around 39%. The first criteria to declare the trial successful is to test if the CR rate with sabatolimab in combination with azacitidine and venetoclax is at least 50% (statistical significance).

The Bayesian formulation of this dual criterion design can be expressed as below:

- Bayesian statistical significance: probability for a positive treatment effect (i.e. CR rate > 39% | data) ≥ 0.975.
- Clinical relevance: posterior median of CR rate \geq 50%.

With two criteria stated above the minimally required sample (n_{min}) size is 67 and the sample size was set to 70 including participants from cohort 2 of the Safety run-in (Part 1) and the Expansion (Part 2) and thus 76 for the total sample size (including the 6 participants treated at 400 mg Q4W in the cohort 1 of the Safety run-in (Part 1). For 70 participants (included for the primary efficacy analysis), the table below shows data scenarios (number of participant achieving complete remission) with respective inferential results and decisions.

The minimum number of participants with CR to declare this trial successful (both statistical significance and clinical relevance met) is 36 out of 70 participants (51.4%).

Based on simulations (Table 12-1), a total of 36 responders out of 70 participants is required for trial success, with estimates of 51.4% for the posterior median CR rate and 98.3% for the posterior probability for a positive effect (CR>39%). If the number of participants with CR is less than 36, both criteria are not met (NO-GO).

True CR rate	Posterior median CR	Posterior probability for a positive effect (CR>39%)	Decision for trial success
30/70 (42.9%)	43.0%	0.754	Failed
31/70 (44.3%)	44.4%	0.823	Failed
32/70 (45.7%)	45.8%	0.879	Failed
33/70 (47.1%)	47.2%	0.920	Failed
34/70 (48.6%)	48.6%	0.950	Failed
35/70 (50.0%)	50.0%	0.970	Failed
36/70 (51.4%)	51.4%	0.983	Successful

 Table 12-1
 Data scenarios, inferential results and decisions (n=70)

A non-informative Beta (1,1) prior with mean 50% has been used in these calculations.

Operating characteristics for various true CR rates are presented in the table below. The type-I error under the null value (CR rate = 38.6%) is 2.0% and power is 80% assuming a true CR of 55.7 %.

True CR rate	Probability of success (Go)	Probability of futility (No Go)
27/70 (38.6%)*	0.020	0.980
28/70 (40.0%)	0.035	0.965
29/70 (41.4%)	0.056	0.944
30/70(42.9%)	0.094	0.906
31/70 (44.3%)	0.140	0.860
32/70 (45.7%)	0.204	0.796
33/70 (47.1%)	0.272	0.728
34/70 (48.6%)	0.355	0.645
35/70 (50%)	0.452	0.548
36/70 (51.4%)	0.546	0.454
37/70 (52.9%)	0.644	0.356
38/70 (54.3%)	0.721	0.279
39/70 (55.7%)**	0.800	0.200

Table 12-2Operating characteristics for true CR rate (n=70)

*For a true CR rate of 38.6% (null value), the probability for a trial success is 2.0% (*type-I error*). **For a true CR rate of 55.7%, the probability for a trial success is 80% (*power*). These calculation were made using the software R (version 3.6.1) using the RBestT package.

13 Ethical considerations and administrative procedures

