	combination with venetoclax and azacitidine will be guided by a Bayesian analysis based on the DLT incidence reported during the two first cycles as well as an overall safety overview. The probability that the true DLT rate is $\geq 33\%$ (i.e. overdose criteria) will be modeled using a Bayesian Model. If the dose of 400 mg Q4W (cohort 1) meets overdose criteria with at least 3 evaluable participants, the study will be stopped. If the dose of 400 mg Q4W does not meet overdose criteria, cohort 2 with sabatolimab 800 mg Q4W will be opened with approximately 12 participants. If the dose of 800 mg Q4W meets overdose criteria with at least 9 evaluable participants, Part 2 (Expansion) will not be opened and the study will be stopped. Otherwise, Part 2 (Expansion) will be opened at 800 mg Q4W of sabatolimab (see Figure 3-1).
	For all participants treated with sabatolimab at 800 mg Q4W, the efficacy of sabatolimab in combination with venetoclax and azacitidine will be based on the proportion of participants achieving a complete remission (CR) as per investigator assessment. Trial success will be assessed based on dual decision criterion with a null value (no effect) of 39% (statistical criteria) and a minimum estimated effect size (clinical relevance) of 50% (clinical criteria) for the CR rate. If the statistical and clinical criteria are both met, the trial will be declared successful.
	With two criteria stated above, approximately 70 participants (including participants from cohort 2 of the Safety run-in (Part 1) and Expansion part) are required. Therefore, the total sample size is 76 participants (including the 6 participants treated at 400 mg Q4W in the Cohort 1 of the Safety run-in (Part 1)).
	AL least thirty six participants with CR out of 70 are needed to declare the trial successful.
	For a true CR rate of 55.7% (i.e. 39 participants with CR), the probability for the trial success is 80% (power).
Key words	Phase II, sabatolimab, TIM-3, venetoclax, azacitidine, Myelodysplastic syndromes (MDS).

1 Introduction

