12.4.2.2 Cohort 2 of Safety run-in (Part 1) and Expansion (Part 2)

CR primary analysis

The CR primary analysis will be performed for participants from cohort 2 of Safety run-in (Part 1) and Expansion (Part 2) treated with sabatolimab 800 mg Q4W.

A Bayesian design will be used in order to estimate the CR rate in the FAS (Full Analysis Set) and to provide inferential summaries (e.g., mean, median, standard deviation, 95% credible intervals, and interval probabilities) based on Bayesian posterior distribution of the CR rate. Assuming a non-informative prior distribution (Beta(1,1)), the distribution of the CR rate will be updated with all available data from the participants included in the FAS.

The decision criteria for trial success are the following:

- Posterior median of CR rate is \geq 50% and
- Posterior probability that CR rate is > 39% is at least 97.5%.

The cumulative posterior distribution will be used to derive the probability that the true CR rate is superior to 50%. Based on preliminary efficacy data observed with the combination azacitidine + venetoclax (Wei et al 2019), a 50% CR rate is a reasonable threshold to be considered in this specific setting.

The results will be also presented with a frequentist formulation. The CR rate and the exact 95% confidence interval (CI) (Clopper CJ and Pearson ES 1934), as well as the 1-sided p-value will be provided on the FAS. The test will be performed using an overall one-sided 2.5% level of significance. Thus, the null hypothesis (H₀:CR \leq 39%) will be rejected if the lower bound of the two-sided 95% exact CI is >39%.

The analysis will be performed using data up to the analysis data cut-off date, which will be 6 cycles after the last participant is enrolled.

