2.5.2.2 Cohort 2 of Safety run-in (Part 1) and Expansion (Part 2)

CR primary analysis

As Novartis decided to halt the enrollment in the expansion part, only the CR rate by the dose level of sabatolimab with exact 95% confidence interval will be reported in the abbreviated CSR.

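### The quoted type-I error of 2.0% belongs to a CR rate of 38.6%; at the declared null of 39% the rule of at least 36 of 70 gives 2.3%, and two nearby sentences misstate the dual criteria

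*Protocol*

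**What the plan says.** The protocol summary sets the null: "Trial success will be assessed based on dual decision criterion with a null value (no effect) of 39% (statistical criteria"), together with "a minimum estimated effect size (clinical relevance) of 50% (clinical criteria) for the CR rate". Protocol section 12.4.2.2 uses the same two thresholds. Success needs a posterior median of at least 50% and a posterior probability of at least 97.5% that the CR rate exceeds 39%. In the frequentist version, the null hypothesis of a CR rate of 39% or less "will be rejected if the lower bound of the two-sided 95% exact CI is >39"%, at a one-sided 2.5% level.

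The sample-size section (Protocol 12.8.1.2, repeated in SAP 2.9.2) differs in three places:

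- On type-I error it says "The type-I error under the null value (CR rate = 38.6%) is 2.0"%. The footnote to Table 12-2 (Table 2-6 in the SAP) repeats it: "For a true CR rate of 38.6% (null value), the probability for a trial success is 2.0"%.
- On the first success criterion it says the test is whether the CR rate "is at least 50% (statistical significance"). The bullets directly below give 39% to statistical significance and 50% to clinical relevance.
- On failure it says "If the number of participants with CR is less than 36, both criteria are not met (NO-GO"). Table 12-1 (Table 2-5 in the SAP) shows a posterior median of 50.0% and a posterior probability of 0.970 for 35/70.

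The SAP was written after the recruitment halt. Its section 2.5.2.2 says "only the CR rate by the dose level of sabatolimab with exact 95% confidence interval will be reported in the abbreviated CSR", and its section 3 lists the primary CR analysis among those not performed.

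**The concern.** The null hypothesis covers every CR rate up to and including 39%. The chance of reaching 36 CRs rises with the true rate, so the type-I error of the rule is its value at 39%, the edge of that region. A figure taken at 38.6% lies inside the region and must be smaller. Calling 38.6% the null value therefore understates a headline operating characteristic.

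The other two sentences matter because they sit in the section that defines trial success. Read literally, one moves the tested value from 39% to 50%. The other denies what the table shows for the result one CR short of success.

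**Working it through.** **Inputs.** n = 70, success at 36 or more CRs, Beta(1,1) prior, thresholds 39% with 0.975 and 50% for the posterior median, alternative 39/70 = 55.7% (Protocol 12.4.2.2 and 12.8.1.2). The declared null is 39% (protocol summary and 12.4.2.2).

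**1. Is 36 the right boundary?** With r CRs the posterior is Beta(r + 1, 71 − r).

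| CRs | Posterior | Median | P(CR rate > 39%) | Exact 95% lower limit |
|---|---|---|---|---|
| 35/70 | Beta(36, 36) | 50.0% | 0.970 | 37.80% |
| 36/70 | Beta(37, 35) | 51.4% | 0.983 | 39.17% |

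Yes. The Bayesian rule and the exact test both first succeed at 36. Beta(36, 36) is symmetric, so its median is exactly 50%. The clinical criterion (at least 50%) is therefore met at 35/70, and only 0.970 < 0.975 fails.

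**2. Reproducing the plan's figures.** The probability of success at true rate p is P(X ≥ 36), the sum over x = 36 to 70 of C(70, x) p^x (1 − p)^(70 − x).

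| True CR rate | Exact P(X ≥ 36) | Plan |
|---|---|---|
| 27/70 | 0.0195 | 0.020 |
| 0.386 | 0.0197 | 0.020 |
| 39/70 | 0.8005 | 0.800 |

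All 13 rows of Table 12-2 agree with the exact values to within 0.006. The rule and the table are sound.

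**3. The declared null.** The table's rates step by 1/70. Since 0.39 × 70 = 27.3, 39% falls between the rows for 27/70 and 28/70 and has no row of its own. Evaluating it directly:

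P(X ≥ 36 | n = 70, p = 0.39) = 0.0233.

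The gap from the printed figure is 2.33 − 2.0 ≈ 0.3 percentage points.

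**4. Sensitivity to n (secondary).** The target is approximately 70, so neighbouring sizes are worth a look.

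| n | Minimum CRs, Bayesian rule | Minimum CRs, exact test | Type-I error of Bayesian rule at 39% |
|---|---|---|---|
| 68 | 35 | 35 | 2.47% |
| 69 | 35 | 36 | 3.17% |
| 70 | 36 | 36 | 2.33% |
| 71 | 36 | 37 | 2.98% |
| 72 | 37 | 37 | 2.20% |

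This is not an error in the plan, which ties the 2.5% level to the exact test and tabulates the rule only at 70. It does show that the 2.3% belongs to n = 70 and does not carry over to adjacent sizes.

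**The case against.** The best defence is that this is a labelling slip and not a miscalculation. The text says openly that its 2.0% refers to 38.6%, the figure is correct there, 27/70 is the nearest row to 39%, and 38.6% rounds to 39%. Failure of both criteria could be read loosely as failure to meet both together, and the table marks 35/70 as failed in any case. The sentence about 50% is put right by the bullets beneath it. The analysis has also been dropped.

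Much of this stands. The computation at 38.6% is correct, the decision at every count is clear from the table, and no reported analysis depends on these lines. It does not rescue the wording. The text presents 38.6% as the null value, and the plan's null is 39%. The literal statement about both criteria is untrue at 35/70. No reading reconciles a 50% significance threshold with the bullets that follow. The material on other sample sizes is an aside and not needed for the correction.

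**Conclusion.** The point holds and is minor. At the declared null of 39%, the type-I error of the rule is 2.33%, against the stated 2.0%. The two sentences on the dual criteria contradict the plan's own table and definitions.

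Error control is intact, since 2.33% is below the one-sided 2.5%. The boundary of 36, the sample size of 70 and the 80% power are unaffected. This rests on exact binomial calculation with exactly 70 participants in the analysis and on reading 39% as the null, which the protocol states repeatedly. The practical effect is confined to the design documentation, because the abbreviated report gives only the CR rate with its exact interval. The SAP nevertheless reprints the text and tables uncorrected.

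**What to change.** In Protocol 12.8.1.2 and SAP 2.9.2:

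- State the type-I error as 2.3% at a CR rate of 39%, with power of 80% at 55.7%.
- Add a row to Tables 12-2 and 2-6 for 39.0%, marked as the null value, with 0.023 for success and 0.977 for failure. Remove the null-value footnote from the 38.6% row.
- Say that with fewer than 36 CRs at least one criterion is not met.
- Describe the first criterion as a CR rate greater than 39% (statistical significance) and the second as a posterior median of at least 50% (clinical relevance).

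Keep the prespecified criteria as they are. If the rule were ever applied at an n other than 70, report its boundary and its type-I error at 39% for that n. A short pointer from SAP 2.9.2 to SAP section 3, saying that the rule is not applied after the halt, would help the reader but is optional.

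The cost is a few words and one table row in each document, with no change to design or analysis. If no further protocol amendment is planned, correcting SAP 2.9.2 is enough, since the SAP governs the abbreviated report.

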13.1 Regulatory and ethical compliance

This clinical study was designed and shall be implemented, executed and reported in accordance with the ICH Harmonized Tripartite Guidelines for Good Clinical Practice, with applicable local regulations (including European Directive 2001/20/EC, US CFR 21), and with the ethical principles laid down in the Declaration of Helsinki.

